## Statistical Analysis Plan

The sample-size calculation was based on limited experimental data in a porcine model, and on a consensus decision among expert endosonographers regarding the relative reduction in the time (60%) to deploy preloaded fiducial markers. We estimated that a sample size of 40 patients (20 in each arm) was needed to provide the study with at least 80% power and a 2-sided alpha of 0.05. All analyses were performed according to the intention-to-treat principle. Per-protocol analysis was also performed. Descriptive statistics are reported as absolute values (percentage), mean 2 standard deviation, and median (IQR), as appropriate. Comparisons of baseline characteristics and outcomes were evaluated using chi-square or Fischer exact test for categorical data and Student t test or Mann-Whitney U test for continuous data. Pre-established subgroup analysis was performed by tumor location (head/neck vs body/tail). Although not pre-established in the study protocol, results were also stratified by time of randomization (first half vs second half) to explore a possible learning curve effect. Statistical significance was defined as P <.05. All statistical analyses were performed using Stata/ IC version 12.1 (College Station, TX).

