Factors that could threaten our ability to obtain meaningful generalizable knowledge from this study would be lack of patient followup to reevaluate fiducial marker location. However, as patients are having this procedure performed for cancer therapy, it is unlikely that there will be a large proportion of patients who are lost to followup.

E. Data Analysis Plan. This section should include:

For Quantitative analyses:

i) Statistical Analysis: Categorical variables will be summarized with counts and percentages whereas continuous covariates will be summarized with means and standard deviations (SD). For evaluation of the demographic data a Fisher's exact test or Mann-Whitney U test will be performed as applicable.

ii) Success rates for each of the two arms will be calculated as a proportion of number of successfully deployed fiducial markers over the total number of patients in whom this was attempted within the study population. This will be reported as a percentage. Comparison of successful deployment of fiducial markers by two comparative groups will be performed by Fisher's exact test. Similarly, comparison between the two arms will be performed for technical success, procedure time, adverse event rate, rate of migration, ease of fiducial deployment, and visualization of needle and fiducials via EUS and CT by using Fisher's exact test. When data is ordinal, comparisons will be made using Mann-Whitney U test.

Sample Size:

Sample size calculated for the primary aim showed that in order to detect that the PreLoad4 device can be delivered in at least 60% of the time it takes to deliver a fiducial marker by back-loading, for an 80% power and alpha of 0.05 (two-sided) a minimum of 20 patients will be required in each arm.

Randomization:

Patients will undergo central block randomization (5 blocks of 4 per stratified arm at each center) stratified based on tumor location (head/neck vs. body/tail). This will be performed by a computerized binary number generator at the University of Colorado, who will control randomization for all sites. The arm that the patient will be randomized to will be determined by the above process and with the use of opaque sealed envelopes.

F. Summarize Knowledge to be Gained.

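### The SAP splits results by tumour location and by time of randomization but names no test or estimate of whether the device effect differs between the groups, and the protocol's analysis plan does not contain the location subgroup.

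*SAP*

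**What the plan says.** The SAP (Statistical Analysis Plan) reports two splits of the data. For location it says "Pre-established subgroup analysis was performed by tumor location (head/neck vs body/tail"). For time, it says that "results were also stratified by time of randomization (first half vs second half) to explore a possible learning curve effect", and it states openly that this second split was not in the protocol.

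The SAP's methods are chi-square or Fisher exact tests for categorical data and Student t or Mann-Whitney U tests for continuous data, with one general rule: "Statistical significance was defined as P <.05". It does not say how the groups within a split were compared. It mentions no interaction test, model, stratum-specific interval or multiplicity rule.

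In the protocol (section 2), randomization is "stratified based on tumor location (head/neck vs. body/tail"), and tumour location is also listed as a demographic data item. The Data Analysis Plan (2.E) covers descriptive summaries, Fisher and Mann-Whitney comparisons of the arms, sample size and randomization. It contains no subgroup analysis.

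**The concern.** A location subgroup and a learning-curve analysis both ask whether the effect of the device differs between groups. A two-sample test inside each group does not answer that. It asks whether the effect differs from zero in that group, and with about half the patients the answer depends heavily on chance.

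With 40 patients, a result that is significant for head/neck and not for body/tail, or in one half and not the other, could be read as a device that helps only some tumours or as evidence of learning. If chance often produces that pattern when the effects are identical, such a reading is unsafe.

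A second matter is the word pre-established. The SAP judges the time split against the protocol and reports that it was not planned there. By the same standard the location subgroup is not planned in 2.E either. A reader gives more weight to a subgroup that is described as planned in advance.

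**Working it through.** **Inputs.**
- Two-sided alpha 0.05, 80% power, 20 per arm. The protocol has "for an 80% power and alpha of 0.05 (two-sided) a minimum of 20 patients will be required in each arm", and the SAP has "a sample size of 40 patients (20 in each arm) was needed" for "at least 80% power and a 2-sided alpha of 0.05".
- SD of procedure time: not given in either document.
- Group sizes by location: not given. I assume 10 per arm in each group and vary this up to 16 and 4. The time halves give about 10 per arm each.
- The true effect and SD are taken as the same in both groups, which are independent.

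**The plan's own figure.** The sample size of 20 per arm cannot be reproduced forward without an SD. Solving backwards, 80% power at 20 per arm needs a standardised effect d = 0.886 (normal approximation) or 0.909 (noncentral t). That implies an SD of 44–45% of the control mean for a 40% reduction, or 66–68% for a 60% reduction. I use d = 0.909.

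**Power within a group.** The noncentrality is d × √(n/2), on 2n − 2 degrees of freedom.
- n = 20: 0.909 × √10 = 2.875, power 80% (the starting point).
- n = 10: 0.909 × √5 = 2.033, power 48.6%.
- n = 14: power 63.9%. n = 6: power 29.7%.

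**Chance that exactly one group reaches P <.05 when the effects are identical.** With powers p and q this is p(1 − q) + q(1 − p).
- Even split: 2 × 0.486 × 0.514 = 0.50.
- 70:30 split (14 and 6 per arm): 0.639 × 0.703 + 0.297 × 0.361 = 0.56.
- 12 and 8 per arm: 51.4%. 16 and 4 per arm: 62.4%.

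Simulation at the even split gave 49.7% with t tests (10,000 trials) and 48.8% with Mann-Whitney tests (5,000 trials). Across the location and time splits together, at least one was discordant in 66% of simulated trials.

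**Dependence on the true effect (even split, t test).**

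| True d | Power at 10 per arm | Exactly one significant |
|---|---|---|
| 0 | 5.0% | 9.5% |
| 0.5 | 18.5% | 30% |
| 0.7 | 31.7% | 43% |
| 0.909 | 48.6% | 50% |
| 1.2 | 71.8% | 40% |
| 1.36 | 82.0% | 30% |
| 1.5 | 88.7% | 20% |
| 2.0 | 98.8% | 2% |

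The value 1.36 comes from the documents' two wordings of the effect. The protocol's hypothesis, read literally, is delivery in 60% of the back-loaded time, a 40% reduction. The SAP speaks of a consensus "regarding the relative reduction in the time (60%) to deploy preloaded fiducial markers". If 20 per arm was sized for a 40% reduction and the truth is 60%, then d = 0.909 × 60/40 = 1.36.

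**Interaction test.** With identical effects its false-signal rate is 5% by construction (simulated 5.2%). With 10 patients in each of four cells, the difference between the two stratum effects has standard error √(4/10) = 0.632 SD. If the effect is 0.909 in one stratum and absent in the other, the noncentrality is 0.909/0.632 = 1.437 on 36 degrees of freedom, giving power of about 29%.

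**The case against.** The strongest reply is that the SAP does not say the groups were tested separately. It says only that a subgroup analysis was performed and results were stratified; the tests and the threshold are general statements. A reader might infer that separate P values were the chosen method. The documents do not establish this, since the groups could have been only described. This stands, and the point is therefore conditional. It does not remove the gap, because no listed method addresses a difference in effects.

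A reader might also infer that identical effects will look different half the time, whatever the truth. That is too strong: 50% is the maximum for equal groups and applies only near the back-solved effect. It falls well below that for much larger effects or none, and unequal groups can exceed it.

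Other parts of the reply also stand:
- The time split is already disclosed as unplanned and exploratory, so the labelling criticism applies to location only.
- A reader might infer that the trial-wide halves mix calendar time with site. Neither document gives site start dates, so staggered opening is only a possibility.
- Location was fixed in advance as a stratification factor, which gives the term pre-established partial support. Choosing a stratification factor is still not the same as planning a subgroup analysis.
- The proposed interaction test has low power. That is a reason to rely on the interval, and it does not justify separate P values.

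**Conclusion.** The point holds in conditional form. The plan reports two sets of subgroup results without a method for saying whether the effect differs between groups. If separate P values are used, identical effects at the design value would give a discordant pair in about 50% of trials (even split) or 56% (70:30), against about 5% for an interaction test.

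These figures assume d = 0.91, back-solved from the power statement, and group sizes that the documents do not give. Over the effects tabulated, the even-split figure runs from 2% to 50%.

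Pre-established is not supported by the protocol text available. Some protocol pages were not available to this review, though the data analysis section was.

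A reader might infer that the main result is in doubt. It is not: these are secondary analyses, and the primary comparison of procedure time does not depend on them.

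**What to change.** 1. For procedure time, fit log time on treatment, tumour location and their interaction. Report the time ratio with its 95% CI in each stratum, and the interaction estimate with its CI, in place of within-group P values.
2. Label the location subgroup exploratory, or cite the document and date in which it was pre-specified.
3. For the learning curve, replace the two halves with a treatment-by-case-order interaction. Take the order from procedure dates within site. The randomization list cannot supply it, because it runs in separate location strata at each center.

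The cost is a revision of the SAP wording and one or two models. Location should be on hand as the stratification factor; procedure dates must be retrieved if they are not already in the data. There are two downsides. Interaction power is only about 29% even if the effect is absent in one stratum, so the intervals matter more than the P value. Case order within site also counts cases with both devices, so it is an imperfect measure of experience with the new one.

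### Results are split by tumour location and by randomisation half, but the plan gives no test or estimate of whether the needle effect differs between the strata

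*SAP*

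**What the plan says.** The Statistical Analysis Plan section of the SAP contains two splits of the data. For location it states "Pre-established subgroup analysis was performed by tumor location (head/neck vs body/tail". For time it states "results were also stratified by time of randomization (first half vs second half) to explore a possible learning curve effect", and it acknowledges that this second split was not planned in the protocol.

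The tests it names are chi-square or Fisher's exact for categorical data and "Student t test or Mann-Whitney U test for continuous data". Significance is a P value below 0.05, with no separate rule for subgroups.

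The protocol's Data Analysis Plan (section 2, part E) names only Fisher's exact and Mann-Whitney tests. It uses tumour location as a randomisation stratum and describes no subgroup analysis. Neither document mentions an interaction term, a regression model, or a confidence interval for the difference in effect between strata.

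On size, the SAP says "We estimated that a sample size of 40 patients (20 in each arm) was needed" to give "at least 80% power and a 2-sided alpha of 0.05". The protocol's sample-size paragraph is consistent with this: "for an 80% power and alpha of 0.05 (two-sided".

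**The concern.** The natural use of these splits is to ask whether the time saved with the preloaded needle depends on where the tumour lies, or changed as operators gained experience. The matching null hypothesis is that the arm effect is the same in both strata. A two-arm test inside one stratum has a different null, namely that the arms do not differ in that stratum.

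A reader given one P value per stratum can only note that one is below 0.05 and the other is not. In small strata that pattern mostly reflects power. What is at stake is a statement such as benefit only for head/neck tumours, or benefit only after a learning period, when nothing varies between the strata.

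**Working it through.** **1. The plan's own figure.** The inputs are 20 per arm, 80% power and two-sided alpha 0.05, from both documents. Neither document gives an SD. The planned effect is worded differently in the two: the SAP has "the relative reduction in the time (60%) to deploy preloaded fiducial markers", while the protocol has "60% of the time it takes to deliver a fiducial marker by back-loading", which is a 40% reduction. So 20 per arm cannot be reproduced from stated inputs, but it can be solved backwards for the standardised effect d:

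- Normal approximation: d = (1.960 + 0.842) × √(2/20) = 0.886.
- Noncentral t, 38 df: d = 0.909.

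Because d is solved from the power, it does not depend on which wording is used; the unstated SD absorbs the difference (0.40/0.886 = 0.45 of the control mean, or 0.60/0.886 = 0.68).

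**2. Same effect in two equal strata.** With 10 per arm in each stratum, the noncentrality is 0.909/√(2/10) = 2.03 on 18 df, so power per stratum is p = 0.486. The chance that exactly one stratum is significant is 2p(1 − p) = 2 × 0.486 × 0.514 = 0.50. The pattern of second half significant and first half not takes half of this, 0.25.

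**3. Unequal strata, same d.** The location split is not in the documents, so these splits are assumptions. The formula is p₁(1 − p₂) + p₂(1 − p₁).

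| Per arm | p₁ | p₂ | Exactly one significant |
|---|---|---|---|
| 10/10 | 0.486 | 0.486 | 0.50 |
| 12/8 | 0.567 | 0.395 | 0.51 |
| 14/6 | 0.639 | 0.296 | 0.56 |
| 16/4 | 0.701 | 0.192 | 0.62 |

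At 14/6, only the larger stratum is significant in 0.639 × 0.704 = 45% of trials, and only the smaller in 0.296 × 0.361 = 11%.

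**4. Sensitivity to the true effect, equal strata.**

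| Overall power | d | Power per stratum | Exactly one significant |
|---|---|---|---|
| 50% | 0.636 | 0.270 | 0.39 |
| 80% | 0.909 | 0.486 | 0.50 |
| 90% | 1.052 | 0.605 | 0.48 |
| 95% | 1.170 | 0.697 | 0.42 |
| 99% | 1.391 | 0.837 | 0.27 |
| 99.9% | 1.640 | 0.934 | 0.12 |

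Put another way, assume an SD of 0.3 to 0.7 of the control mean. The range is then 0.31-0.49 for a 40% reduction and 0.02-0.49 for a 60% reduction. If the needles do not differ at all, it is 2 × 0.05 × 0.95 = 0.095.

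**5. Simulation check.** In 4,000 trials with a constant effect of d = 0.909 and equal strata, exactly one location stratum was significant in 49% (t test) or 48% (exact Mann-Whitney), and exactly one time half in 50% (t test). At least one of the two analyses was split in 66%. An arm-by-stratum interaction test at 0.05 was significant in 4.8% for location, and in 9.7% for at least one of location and time.

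**6. What the interaction test can detect.** With 10 per arm per stratum, the difference between two stratum effects has standard error √(4/10) = 0.632 SD units.

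- Difference equal to the design effect: 0.886/0.632 − 1.960 = −0.56, so power is 29%.
- Difference of twice the design effect: 1.772/0.632 − 1.960 = 0.84, so power is 80%.

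**The case against.** The strongest reply is that the SAP does not say how strata will be compared. Its test list covers baseline characteristics and outcomes in general, and the sentences on the two splits name no test and no decision rule. A reader might infer that the sponsor planned to claim a location or learning effect whenever one stratum's P value falls below 0.05 and the other's does not. The documents do not say that, and it should not be attributed to them. What stands is that the plan offers no other tool.

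The time split can also be read in two ways. Comparing first-half with second-half times within each arm would ask whether operators got faster with a given needle, and a two-group test suits that question. It would still not show whether the difference between needles changed.

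The 50% figure is conditional. The SAP says at least 80% power and gives no SD, so a larger standardised effect is possible and would lower the figure, as step 4 shows.

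Unequal location strata are not documented either. The protocol's block plan provides the same number of blocks for each stratum at each centre, so a statement that the smaller stratum will look unresponsive needs an assumed split.

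Finally, the time split is already described as an exploration outside the protocol. That lessens its weight without supplying the missing contrast. The location split carries no such label.

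**Conclusion.** The point holds as a gap in the plan: results are divided by two factors, and nothing specified tests or estimates whether the arm effect differs between the parts. The risk of about 50% per analysis rests on three assumptions: the strata are read by their separate P values, the true effect is the one giving 80% power at 20 per arm, and the strata are equal. Over overall power of 50-95% with equal strata it stays at 39-50%; at 99% it is 27%. At the 80%-power effect, the assumed unequal splits give 51-62%. An interaction test would give about 5%.

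Two stronger readings are not supported: that the plan commits to comparing P values between strata, and that a constant effect will look variable half the time whatever its size. The primary comparison and the sample size are not affected. This is an inexpensive improvement to two secondary analyses.

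**What to change.** For placement time, the primary outcome, fit a linear model of log time on arm, stratum and arm-by-stratum interaction, once with tumour location and once with randomisation half as the stratum. Report:

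- the ratio of times between arms, with 95% CI, in each stratum;
- the ratio of those two ratios, with its 95% CI and the interaction P value.

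State that any claim that the device comparison varies by location or with learning rests only on that contrast, and label both analyses exploratory. The log scale matches the protocol's hypothesis of a proportional saving. The model covers time only. If other outcomes are split, give stratum estimates with CIs and make no claim from differing stratum P values.

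The cost is a few sentences in the SAP and a few lines of code, with no new data or patients. The downside is imprecision: at 40 patients the interaction has about 29% power for a between-stratum difference as large as the design effect, and reaches 80% only at twice that. The interval must carry the message, and fewer subgroup claims will be possible.

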1.2 Hypotheses and Endpoints

Hypotheses

- 1) Use of a 22 G preloaded needle for EUS guided fiducial marker placement in patients with pancreatic cancer will be delivered in at least 60% of the procedure time that it takes for traditional back-loaded 22G needles, improving overall procedure efficiency.
- 2) Use of a 22 G preloaded needle for EUS guided fiducial marker placement in patients with pancreatic cancer will maintain comparable technical success and adverse event rates when compared to traditional back-loaded 22G needles.

Primary Aims

1) To compare the procedure time of 22G needle placement of three Visicoil fiducial markers and 22G needle preloaded fiducial markers.

Secondary Aims

1) To compare endpoints of technical success defined as proper placement of three fiducial markers in a pancreatic neoplasm in 22G needle placement of Visicoil fiducial markers and 22G needle preloaded fiducial markers.

2) To compare adverse event rates in 22G needle placement of Visicoil fiducial markers and 22G needle preloaded fiducial markers

1.3. Preliminary Studies/Progress Report: To date, there are no preliminary studies of the above proposed study.

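### One unqualified P < .05 rule covers procedure time and nine or ten unadjusted secondary comparisons that are not labelled exploratory

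*SAP*

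**What the plan says.** The SAP's rule is "Statistical significance was defined as P <.05". The paragraph that contains it applies tests to baseline characteristics and to outcomes in general. It makes intention-to-treat the principle for all analyses and adds "Per-protocol analysis was also performed". It also includes a planned subgroup analysis by tumor location and an unplanned split by first and second half of randomization.

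The protocol ties its error rate to one aim. Under Sample Size it begins "Sample size calculated for the primary aim showed that in order to detect that the PreLoad4 device can be delivered" and continues "for an 80% power and alpha of 0.05 (two-sided) a minimum of 20 patients will be required in each arm". That aim is procedure time, the single primary endpoint in section 1.2 and in the Endpoints list of section 2.

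The Data Analysis Plan (section 2.E, ii) nevertheless puts procedure time in one testing sentence with the secondaries: "comparison between the two arms will be performed for technical success, procedure time, adverse event rate, rate of migration, ease of fiducial deployment", followed by needle and marker visualization. Fisher's exact test is named for these comparisons and the Mann-Whitney U test for ordinal data. Neither document sets an order of testing among the secondaries, adjusts for their number or calls them exploratory.

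**The concern.** A threshold with no named endpoint lets any secondary comparison that falls below it be reported as statistically significant. The 0.05 was chosen for one sized comparison. Applied separately to nine or ten others in a 40-patient trial, it gives a chance well above 5% that at least one looks like a real difference between needles when there is none.

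Several of these outcomes are ratings of ease or visibility. A chance difference on one of them could be presented as a demonstrated property of the new needle, without the support that the primary comparison has from its sample size.

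**Working it through.** **The plan's own figures.** The documents state no error rate for the set of tests, so there is none to reproduce. The sample size of 20 per arm enters below only through Fisher's test. It cannot be reproduced, because no standard deviation is given: 20 per arm at 80% power needs a standardized difference of (1.960 + 0.842) × √(2/20) = 0.886. This does not affect the present point.

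**Number of secondary comparisons.**
- The Endpoints list in section 2 has eight: technical success, migration, ease of passage, ease of deployment, EUS appearance of the markers, radiation oncology visualization, inadvertent deployment and adverse events. The comparison across sites is descriptive and is not counted.
- The Protocol Summary adds visualization of the needle, which makes nine.
- Section 2.E, ii) compares successful marker deployment separately from technical success, which makes ten.

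**Upper figure: independent tests, each of exact size 5%, intention-to-treat, no true differences.** The chance of at least one P < .05 among k tests is 1 − 0.95^k. A two-sided test puts 2.5% in each direction, so the chance of at least one result favouring the new needle is 1 − 0.975^k.

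| Tests | Either direction | Favouring the new needle |
|---|---|---|
| Procedure time alone | 5.0% | 2.5% |
| 9 secondaries | 1 − 0.95^9 = 37.0% | 1 − 0.975^9 = 20.4% |
| 10 secondaries | 1 − 0.95^10 = 40.1% | 1 − 0.975^10 = 22.4% |

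**Allowing for Fisher's test.** Full enumeration at 20 per arm gives a true size of 0.19%, 1.18% and 2.26% at event rates of 5%, 10% and 20%. Take nine secondaries as five ordinal items at 5% and four binary outcomes with assumed rates of 5%, 10%, 10% and 20%, all independent:
- Either direction: 1 − 0.95^5 × 0.9981 × 0.9882² × 0.9774 = 26%.
- Favouring the new needle, with each size halved: 1 − 0.975^5 × 0.9991 × 0.9941² × 0.9887 = 14%.

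**Allowing for correlated ratings.** In simulation with five 5-level items by Mann-Whitney and four binary outcomes (rates 5–20%) by Fisher, at least one P < .05 occurs in 25.7%, 22.7% and 20.5% of trials for correlations between ratings of 0, 0.3 and 0.6. Half of the lowest figure is about 10%.

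**Choice of test.** The SAP also permits chi-square, with no rule for choosing it. Its uncorrected size at 20 per arm is 1.2%, 3.9% and 5.0% at the same event rates. The nine-test figure then becomes 1 − 0.95^5 × 0.988 × 0.961² × 0.950 = 33%.

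**Not counted.** None of these figures includes per-protocol repeats, tumor-location strata or the first-half/second-half strata.

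**The case against.** The strongest reply is that the protocol already separates one primary endpoint from the secondaries and ties alpha and power to it. A careful reader would treat the secondaries as supportive, and the primary error stays at 5% whatever they show. That stands, and it limits the point to the secondaries. It does not remove the point, because the SAP's rule makes no such distinction.

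Three stronger readings are tempting, and the documents do not support them:
- *A chance advantage for the new needle is likely.* It is not. Two-sided tests put about half the error in that direction: 22% at most for ten independent tests, and about 14% once Fisher's conservatism is allowed for.
- *Every secondary is tested twice, by intention-to-treat and per-protocol.* The SAP says only "Per-protocol analysis was also performed" and does not say for which outcomes. The two sets would also share most patients, so repeats would not double the number of independent tests.
- *The primary result is compromised.* It is not, for the reason given above.

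Other objections stand in part. Ten tests requires counting marker deployment apart from technical success, and those two are closely related. The event rates and the five ordinal items are assumptions. The only relevant rate in the protocol is technical success of 86–100%, that is 0–14% failure, a range in which Fisher's test is conservative. For technical success and adverse events the hypothesis is comparability, with no margin, so the main risk there is reading non-significance as comparability. Finally, the SAP is written in the past tense, so a new label would work as a caveat on reporting rather than as prespecified error control.

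**Conclusion.** The concern holds for the secondary endpoints. Nine or ten comparisons share an unqualified 0.05 threshold with no adjustment and no exploratory label. With equivalent needles, the intention-to-treat chance of at least one false-positive secondary is 37–40% under independence at exact 5%, and roughly 20–26% with Fisher's test and correlated ratings. The portion favouring the new needle is roughly 10–22%. The lower ranges rest on the assumed event rates (5–20%), five ordinal items and correlations of 0 to 0.6; chi-square tests would raise them. The absence of any adjustment or label does not depend on these assumptions. The point ranks as a cheap improvement.

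**What to change.** In the SAP, replace the significance sentence with wording such as:

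> P < .05 (two-sided) is confirmatory only for the intention-to-treat comparison of procedure time. Secondary endpoints, tumor-location subgroups and the first-half/second-half analysis are exploratory. They are reported as between-arm estimates with 95% confidence intervals, and any P values are unadjusted. Per-protocol results are sensitivity analyses.

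Align section 2.E, ii) of the protocol, so that its Fisher and Mann-Whitney tests of secondaries carry the same label and procedure time is set apart. The SAP already describes the first-half/second-half split as unplanned and exploratory in purpose; the new wording should cover it all the same. The between-arm estimate for ordinal ratings also needs to be named.

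If confirmatory claims on secondaries are wanted, the alternative is an adjustment. Bonferroni, or the first Holm step, over nine secondaries gives 0.05/9 = 0.0056, a demanding threshold with 20 patients per arm.

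The recommended change needs no patients and no new data. Its cost is that no secondary endpoint can support a confirmatory claim of significance.
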